2 BACKGROUND INFORMATION AND SCIENTIFIC RATIONALE

2.1 Background Information

Bipolar disorder is a disorder that causes unusual shifts in mood and can cause cognitive dysfunction, poor function in daily living and an inability to carry out day-to-day tasks. Bipolar disorder currently affects approximately 5.7 million American adults. Although a substantial amount of literature has examined both manic and depressive states in bipolar disorder, there is relatively little information about the cognitive and neurophysiological functioning of bipolar patients when they are in a euthymic or stable state. This proposed research study will examine the cognitive and neurophysiological functioning of euthymic patients with bipolar disorder. Additionally, this study will examine the effects of cognitive training on cognitive and neurophysiological abnormalities in euthymic adults with bipolar disorder. It is imperative to not only develop a neurocognitive profile of stable bipolar patients but also to understand ways in which training can improve both cognitive and neurophysiological outcomes for these patients.

Cognitive deficits such as executive function, attention, memory and processing speed have been shown in bipolar patients in euthymic, manic, and depressive states (Gruzelier et al., 1988; Murphy et al., 1999; Sweeney et al., 2000; Bearden et al., 2001; Clark et al., 2002; Quraishi and Frangou 2002; Seidman et al., 2002; Martínez-Arán et al., 2004; Savitz et al., 2005; Pavuluri et al., 2006; Schretlen et al., 2007; Sanchez-Morla et al., 2009). Additionally, studies solely conducted with euthymic bipolar patients have shown impairments in information processing strategies, synthesizing information, abstraction abilities and visuospatial abilities (Clark et al., 1985; Sapin et al., 1987; Tham et al., 1997). Although the aforementioned studies have shown clear cognitive deficits associated with bipolar disorder, there has yet to be a consensus of a cognitive profile of bipolar disorder, specifically in the euthymic state. Characterizing cognitive dysfunction in euthymic bipolar patients would inform cognitive training programs on what abilities should be targeted for intervention.

Patients with bipolar disorder have also been shown to have structural and functional deficits in specific brain regions such as increased left ventricular size, increased amygdala size, disruptions in white matter, and decreased activity in the prefrontal cortex (Drevets et al., 1997; Altshuler et al., 1998; Strakowski et al., 1999; McDonald et al., 2005; Mahon et al., 2009). Structural abnormalities in bipolar patients could be the cause of cognitive and functional deficits in memory and executive function but have yet to be linked. Also, large-scale neural networks, such as the default mode network (DMN), have shown differential activation in bipolar patients versus normal controls (Calhoun et al., 2009; Whitefield-Gabrieli & Ford, 2012). Understanding the structural and functional abnormalities associated with bipolar disorder could lead to a theoretical model of a brain basis for mood disorders.

2.2 Scientific Rationale

Training programs that have attempted to mitigate cognitive and functional deficits in patients with bipolar disorder have largely been limited to cognitive behavioral therapy (CBT) techniques and have focused more on improving daily living than improving cognitive or brain function (Scott, Garland & Moorehead, 2001; Scott et al., 2006). Although these studies have found that CBT has a significant effect in improving daily living and mood episodes, it is still unclear if training can mitigate the cognitive deficits seen in bipolar patients. Preliminary evidence highlights the potential of reasoning training as well as physical training to modify and strengthen brain and cognitive function in healthy adults as well as patient populations. Evidence from our lab indicates that frontally mediated, gist-based reasoning (defined as the ability to combine detail information to construct abstract meanings) offers a promising cognitive domain to train in many different populations including seniors, veterans, and traumatic brain injury patients. Furthermore, previous studies from our lab have shown that our gist-reasoning training improves cognitive functions in both trained and untrained areas as well as increases brain-blood flow, white matter diffusivity and functional connectivity. As our gist-reasoning training targets cognitive functions such as integrated reasoning and strategic attention, which are known to be impaired in bipolar patients, it is possible that this training would greatly enhance the cognitive and neural functioning of adults with bipolar disorder.

2.3 Potential Risks and Benefits

2.3.1 Potential Risks

There are no known risks associated with the behavioral and psychological testing other than fatigue and frustration. If the participant's responses to questionnaires or the information they provide to study personnel indicate suicidal thoughts or actions, the researchers are obligated to notify authorities. They will refer the participant to a psychiatrist. There is also a risk that bipolar patients may have manic or depressive episodes while undergoing cognitive training. If this is reported to us from the participant, they will be referred to a physician and taken out of the study. There are no known risks or adverse effects resulting directly from exposure to magnetic fields and radio frequency energy used in this study other than a feeling of claustrophobia. As long as the patient has been cleared by the imaging center technicians as safe to go into the magnet, e.g. no pacemaker or incompatible metal in the patient.

Also, the MR scanner produces tapping sounds during operation, which may reach very loud levels. To minimize any discomfort from this noise, the patient will be provided with disposable earplugs or headphones that suppress external noise levels but do not eliminate voice communication with the scanner operator. If the participant is unable to tolerate being in the scanner, we will stop the scan immediately at any time. Other risks of MRI, but that rarely occur: 1) Neurostimulation. In some cases it is possible that the subject might experience neurostimulation effects, such as muscle twitches and tingling sensations, due to the rapid

switching of magnetic field gradients used in these examinations. There are no known risks associated with these effects; 2) Quench Hazard. The MR scanner uses liquid nitrogen and liquid helium. It is remotely possible that the liquid nitrogen and helium will boil off rapidly and fill the magnet room with extremely cold dense gaseous nitrogen and helium, which can be dangerous if breathed for more than a few moments. The scanner operator will obviously detect this and immediately provide assistance to anyone inside the magnet room.

Although there is no evidence of any risk to pregnant women, we will exclude women who are pregnant or suspect they may be pregnant.

The risks associated with specific study procedures will be thoroughly explained to participants. Clinicians will confirm the appropriateness of each participant prior to intervention by phone, and the clinician will check emotional status during weekly sessions of participants. The risks of the cognitive assessment will be mitigated by using highly trained personnel who provide encouragement; schedule breaks, and provide a supportive environment for the study participant. The project staff will explain all procedures, including the time required. Care will be taken to minimize any feelings of anxiety and discomfort that may be aroused. The patients will not be pushed to perform beyond their capacities. They will be encouraged to take breaks if they become tired or frustrated. The participant will have the option to terminate participation at any time during the study. Participants will be checked multiple times for metal or other devices that could pose a danger in the MR environment. Also, participants will be given hearing protection during scanning. During the fMRI, subjects will be able to communicate through the intercom built into the scanner. The procedure will be stopped if the subject is unable to complete the study or shows any signs of intolerance such as frequent movements. Reassurance will be provided as needed and they will be reminded that their continued participation in the study is completely voluntary. In the event of severe adverse effects (e.g. headache, nausea, ear problem due to noise), participants will be removed from the study and appropriate follow-up instituted. Potential to heat tissue is present in all magnetic resonance imaging. The amount of power is monitored with appropriate built-in instrumentation to assure the power and heat absorption is under FDA standards. In any event of system failure or problems scanning will stop.

Any time information is collected; there is a potential risk for loss of confidentiality. Every effort will be made to keep your information confidential; however, this cannot be guaranteed.

2.3.2 Known Potential Benefits

Participants may not benefit from enrolling in this study. However, they may benefit from the intervention sessions by improving their thinking ability, memory and learning skills and by feeling an increase in self-esteem, as a result. They will be not be reimbursed for their time and expenses related to participating in the study. In addition, the information obtained from this pilot study may be of benefit to patients in future, as the investigators may gather more information about the interventional strategies to help bipolar patients.

3 OBJECTIVES

- Examine change in cognitive measures pre-post reasoning training in individuals with Bipolar Disorder
- Examine changes in resting state brain blood flow pre-post reasoning training in individuals with Bipolar Disorder
- Examine correlation between cognitive and brain metrics pre-post reasoning training in individuals with Bipolar Disorder

4 STUDY DESIGN

Participants will only include people who are fluent speakers of English, as not all of the standardized and experimental cognitive tests have been normed for non-English speakers. Participants will be screened for significant medical, neurological, or psychiatric illness other than bipolar disorder. Additionally, two separate cognitive testing and two MRI imaging procedures will be conducted with each participant: one at baseline prior to cognitive training, the second at the end of cognitive training (4 weeks). These testing procedures are explained below.

Each participant will receive an appointment card/schedule of appointments to help them keep track of what is expected of them. During the training program participants will make 1 visit per week for 2 hours each over a 4-week period. Prior to cognitive training, participants' baseline gist and detail processing ability, will be obtained with a battery of cognitive measures.

Structural and functional brain measures will also be obtained. All measurements will be taken again at the endpoint of training. Training effects will be measured behaviorally in trained areas (reasoning & physical) and untrained cognitive areas. Additionally, structural and functional brain imaging will measure changes in cerebral blood flow, global and regional brain volume, white matter tracts, efficiency, activation patterns, and blood oxygenation with a particular focus on changes to frontal regions.

5 Study Population

Our study population for this pilot study will include 20-30 adults diagnosed with bipolar disorder I or II; they will be referred by local treating psychiatrists.

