5.1 Selection of the Study Population

Participants will be recruited from [name] at the University of Texas Southwestern Medical Center, as well as through flyers handed out to members of the community who attend lectures related to brain health and express an interest in future and ongoing research studies, and the Center for BrainHealth website. We will also distribute flyers/Advertisements to UTD main campus, community mental health organizations, local media sources, support groups, and to physicians who express an interest in the study for their patients. Participants will be asked to complete cognitive testing before their cognitive training, complete four weeks (2 hours/session) of gist-based training, and then undergo post-testing using the same measures tested before training.

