6 STUDY PROCEDURES/EVALUATIONS

6.1 Study Procedures

- Screening Session: A research assistant will conduct screening procedures over the phone including a brief medical questionnaire covering their history, current medications and any pre-existing conditions. Prior diagnosis of bipolar disorder and euthymic state will be confirmed with study psychiatrist. Additionally, given that the participant meets the requirements covered by the phone screen, participants will be asked to come to the Center for BrainHealth to complete further cognitive assessments.
- Cognitive Testing Session: A clinician from the Center for BrainHealth will administer a group of standardized and experimental tests to each participant for each of the cognitive testing sessions. This session may last up to 4 hours, depending on the pace of the participant's response times. The intent of the tasks is to assess higher level thinking skills, working memory, and selective learning. The cognitive test battery will include tests like Delis-Kaplan Executive Function System (DKEFS) Color-Word Interference Test, Delis-Kaplan Executive Function System (DKEFS) Card Sorting Test, Test of Strategic Learning (TOSL), Auditory Selective Learning, Wechsler Memory Scale (WMS-III) Logical Memory Subtest, Verbal Problem Solving, Wechsler Adult Intelligence Scale (WAIS) Similarities Subtest, Rey-Osterrieth Auditory Verbal Learning Test (RAVLT), Trails A, Trails B, the Controlled Order Word Association Test (COWAT), Wechsler Memory Scale (WMS-III) Digits forward and backwards, and Framing task.
- fMRI: Participants who qualify for the imaging portion will lie in the scanner while images of their brain will be recorded. Each session will take up to 90 minutes. During the MRI and during the DTI (diffusion tensor imaging) the patient will be asked just to lie still.
- Cognitive reasoning training: The gist-based reasoning training will be delivered in one, two hour session each week over 4 weeks. The strategy instruction is hierarchical and dynamically interdependent, with each strategy building upon previous strategies to transform the concrete meaning into abstracted gist-based meanings through reasoning and inference. Constructing meaning at a higher level of abstraction promotes learning which is more efficient and long lasting.

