7.2 Sample Size Considerations

We piloted n=27 participants and 12 of those who completed brain imaging. This was a sufficient sample size to conduct a pilot-study analysis of cognitive and brain changes in this patient population pre-post reasoning training.

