7.3 Participant Enrollment and Follow-Up

We enrolled 27 participants at baseline and all 27 completed the study. 12 of the 27 also completed brain imaging.

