7.4 Analysis Plan

Statistical analysis plan:

General linear models will be used to assess mean changes cognitive outcomes. In resting state fMRI analysis, we will first identify the spatial extent and BOLD signal time course of the default mode network and central executive network for each subject at each time point (pre- and post-training) using advanced statistical methods like ICA. Then, we will compare networks activation across the two time points of the study using repeated measures general linear modeling. Map-wise corrected false positive rates will be controlled at .05 by Bonferroni correction.

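### Does planning two MRIs for each participant, when only 12 of 27 were imaged, undermine the completion figure or the reading of cognitive change beside brain change?

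*Combined protocol and SAP*

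**What the plan says.** Section 4 (Study Design) states that "two separate cognitive testing and two MRI imaging procedures will be conducted with each participant", one at baseline and one at the end of training. It then says that these procedures are explained further on. Later in the same section, after mentioning structural and functional brain measures, it adds: "All measurements will be taken again at the endpoint of training".

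Section 6.1 (Study Procedures) is narrower: "Participants who qualify for the imaging portion will lie in the scanner while images of their brain will be recorded". Its post-intervention item has patients repeat the fMRI and names no subset. Section 5.1 lists what participants are asked to do, beginning "Participants will be asked to complete cognitive testing before their cognitive training", then training and post-testing, with no mention of imaging. Section 5.2 has no imaging criterion. Section 2.3.1 makes scanning depend on clearance by the imaging technicians, excludes pregnancy, and has the scan stopped if it is not tolerated.

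Section 7.3 reports: "We enrolled 27 participants at baseline and all 27 completed the study". The next sentence reads: "12 of the 27 also completed brain imaging". Section 7.2 gives the same two counts and calls the sample sufficient for a "pilot-study analysis of cognitive and brain changes in this patient population". Section 7.4 says "General linear models will be used to assess mean changes cognitive outcomes" and compares network activation across the two time points with a repeated-measures model. It defines no analysis sets.

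**The concern.** Read literally, Sections 4 and 6.1 describe two designs: imaging for everyone, or imaging for a subset. Two things seem to hang on which is meant.

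The first is completion. If every participant was due two scans, 15 of the 27 did not complete the planned procedures, and full completion is the wrong description. Someone planning a larger study could carry forward the wrong figure.

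The second is whom the results describe. Section 3 includes an objective linking cognitive and brain change. If a mean cognitive gain from 27 people is placed beside a mean brain change from 12, a reader may assume that the 12 gained as much as the 27. Tolerance of the scanner, metal or devices, and movement could all influence who was imaged, and the documents do not compare the 12 with the other 15.

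**Working it through.** **Completion counts.** Inputs are from Section 7.3: 27 enrolled, 27 completed, 12 with completed imaging. The plan states no sample-size calculation, so there is no derived figure to reproduce.

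- Completed imaging: 12/27 = 44.4% (exact 95% CI 25.5% to 64.7%). Without it: 15/27 = 55.6%.
- Under Section 4, 12/27 is the most that can have had all planned procedures.
- Under Section 6.1, the figure depends on the number who qualified, N, which is not reported and lies between 12 and 27. The share of qualifiers without completed imaging is (N − 12)/N: 0% at N = 12, 33% at N = 18, 55.6% at N = 27.

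A clean split of 100% under one section and 44% under the other is therefore not established. Completion of 27/27 under Section 6.1 requires that none of the 15 qualified, and the documents do not say. The confidence interval adds little, because the question is one of definition and not of sampling.

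**Which analyses depend on the reading.**

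| Analysis | Participants usable | Section 4 reading | Section 6.1 reading |
|---|---|---|---|
| Mean cognitive change | 27 | 27 | 27 |
| Pre-post network comparison | those with both scans | 12 | 12 |
| Cognition-brain correlation | those with both kinds of data | 12 | 12 |

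Completed imaging is taken here to mean both scans. No row changes.

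**How far the 12 could differ from the 27 by chance.** Work in units of the SD of cognitive change. For a random draw of 12 from 27 without replacement:

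- SE(mean of 12 − mean of 27) = √(1/12 − 1/27) = √0.0463 = 0.215 SD.
- 95% range: 1.96 × 0.215 = ±0.42 SD.

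For illustration only, take a gain of 0.50 SD in the 27 (an assumption; the documents give no effect size). Gains from 0.08 to 0.92 SD in the 12 would then be unremarkable. This holds for any random 12 of 27 and does not indicate an error in this study.

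**What a separate cognitive model in the 12 would show.** The 95% half-width of a mean change is t/√n:

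- n = 27: 2.056/√27 = 0.40 SD.
- n = 12: 2.201/√12 = 0.64 SD.

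At the illustrative 0.50 SD, the interval in the 12 would be −0.14 to 1.14 SD, which contains both zero and the estimate from the 27. For that interval to exclude the 27-person mean, the two means must differ by at least 0.64 SD. The 27-person mean is a weighted average of the 12 and the 15, so (mean of 12 − mean of 27) = (15/27) × (mean of 12 − mean of 15). A gap of 0.64 SD therefore needs the 12 and the 15 to differ by about 0.64 × 27/15 = 1.15 SD of change. Only very strong selection would show.

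**The case for a change.** The best case for a change is that the conflict is in the current text, that qualification for imaging is left undefined, and that no reason is given for the 15 without completed imaging. They may have been ineligible, declined, or had one scan or none. The protocol's own risk section lists plausible selection mechanisms. The remedy would be cheap: a few sentences, one table and one further run of a model already planned.

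Much of this stands as description. The wording of Sections 4 and 6.1 does not match, the post-intervention item in 6.1 does not help, and the safety conditions in Section 2.3.1 are nowhere labelled as the qualification rule. They also do not explain why as many as 15 were not imaged. It is equally true that the 12 have not been shown to represent the 27.

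The consequences do not stand. Section 4 sends the reader on to the procedures, and given Section 2.3.1 its wording could never have meant a scan for literally everyone. Section 7.3 introduces the imaging count as something additional, directly after the completion count, so nobody is misled about either number. No section sets a mean cognitive gain in 27 beside a brain change in 12 as evidence about the same people; Section 7.2 says only that the sample suffices for a pilot analysis of both. The objective that joins the two outcomes is a correlation, and that is confined to the 12 in any case. The further run in the 12 is harmless, and Section 7.4 does not prevent it, but it corrects no stated error.

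**Conclusion.** No change to the plan is called for. The mismatch is a loose overview sentence qualified by a later operational one, together with missing detail that the authors can supply when reporting: what qualified a participant for imaging, why 15 have no completed imaging (or that this was not recorded), and that the brain and correlation results apply to the 12. A competent analyst would label each result with its own number of participants without being told.

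The cognitive results in the 27 and the correlation in the 12 are unaffected. The 12 might differ from the 27 in mean cognitive change by up to about ±0.42 SD through chance alone, and an added estimate with a half-width of 0.64 SD could rarely show it.

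This rests on three assumptions: completed imaging means both scans, the SD of change is similar in the 12 and the 27, and the 12 approximate a random draw. The third cannot be checked from the documents. If it fails, the case for stating plainly whom the imaging results describe is stronger, but the planned analyses stay the same.

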5.1 Selection of the Study Population

Participants will be recruited from [name] at the University of Texas Southwestern Medical Center, as well as through flyers handed out to members of the community who attend lectures related to brain health and express an interest in future and ongoing research studies, and the Center for BrainHealth website. We will also distribute flyers/Advertisements to UTD main campus, community mental health organizations, local media sources, support groups, and to physicians who express an interest in the study for their patients. Participants will be asked to complete cognitive testing before their cognitive training, complete four weeks (2 hours/session) of gist-based training, and then undergo post-testing using the same measures tested before training.

